- 4) Quality of life as reported by the participant, as measured by the Older People's Quality of Life (OPQOL) Questionnaire.

We hypothesize that the AIMs data will result in fewer transfers to higher levels of care, an increase in average level of home assistance (because problems are identified early), more days in which medication assistance is provided, and improved quality of life for the participant. We chose to focus our study on individuals living alone, since this group is at high risk for loss of independence.

EXPERIMENT 6: LONGITUDINAL EVALUATION OF THE USE OF AIMS IN MAKING TRANSITION DECISIONS

STUDY POPULATION

We will begin enrollment for the validation study in the second year of the award. One hundred and fifty subjects living at a partner community (Willamette View, Rose Villa, Terwilliger Plaza, Mirabella and Mary's Woods, Holladay Park Plaza) will be eligible for inclusion in Specific Aim 3. The study will use a pseudo-randomized design. The 150 subjects will be enrolled into one of three groups of 50:

- 1) installed technology, from which AIMs data will be extracted and provided to the transition team at the facility to aid in transition decisions;
- 2) installed technology, from which AIMs data will be extracted but will not be available to the transition team; and
- 3) no technology.

Groups 1 and 2 will be comprised of existing AIMs participants as well as new recruits from the partner communities. Participants will be randomized into the 2 technology arms.

Group 3 will come from residents at the partner communities who are already being tracked through the ORCATECH repository and will not be approached about the study, except to ask them to fill out the quarterly Older People's Quality of Life (OPQOL) Questionnaire.

Groups (2) and (3) will receive the "standard of care" at their facility – that is, transition decisions will be made without reference to AIMs data.

PROCEDURES

One hundred and fifty subjects will be followed over a thirty month period. The protocol will consist of 4 parts:

- 1) Subject enrollment. (see above)
- 2) Provide AIMs data (using the web tool from experiment 4) for the transition teams. Data will include a summary of the past week and will highlight trends over time including outliers.

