- 3) Ongoing assessment of subjects' health status and need for assistance by the care transition team. The procedures for this are: (1) Regular meetings by the care teams (as currently are done) to review resident health status. For those subjects in group 1, this will include review of the AIMs data as well; (2) Decisions about changes in support or living status for the resident, as are

normally made in these meetings; and (3) Completion of a questionnaire by the care team about what, if any, of the AIMs data influenced their decisions. Changes in support may include increased or decreased assistance with managing medications, additional or reduced home care, and/or a transfer to a different level of assisted living. The date and outcome of each intervention made will be recorded for later analysis. Care transition team members will consent to participate in this way.

4) Annual in-person clinical assessments as per the clinical protocol, as well as quarterly Quality of Life assessments (using the Older People's Quality of Life (OPQOL) Questionnaire).

DATA AND SPECIMEN BANKING

All data created in this study will be stored in the Layton Center/ORCATECH repository (IRB #6845).

DATA MANAGEMENT

Sensor data are time-stamped and stored locally on the sensor computer in a secure, password-protected MySQL (relational) database. Data are encrypted and uploaded from the homes to the OHSU research server on a regular basis, but may also be pulled on demand. Research staff access the data from the central data server at OHSU as well as through the router directly to the sensor and user computers using secure commercial remote-connection software. The data, study cohorts, and remote installations are managed using the ORCATECH Management Console (OMC), which is a password-protected multi-tiered remote monitoring application built from Open Source tools, including Adobe Flex, PHP, and MySQL. This tool allows staff to view subject and home information, track recruitment and subject contacts, track inventory, generate alerts for upcoming scheduled visits, view the “health” of the system (e.g., outages), and look at summaries of the data over time.

WITHDRAWAL OF SUBJECTS

If participants transition into a living situation that we cannot adequately sensor, they will be withdrawn from the study.

Any participants withdrawing from the study may be asked to complete an exit survey.

RISKS TO SUBJECTS

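### No OPQOL form is placed before AIMs data reach the transition team, and the withdrawal rule would end OPQOL follow-up for some participants who move

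*Combined protocol and SAP*

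**What the plan says.** The Approach for Specific Aim 3 lists as outcome 4 "Quality of life as reported by the participant, as measured by the Older People's Quality of Life (OPQOL) Questionnaire", and the hypothesis that follows expects "improved quality of life for the participant".

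Under Experiment 6, Study Population, "The 150 subjects will be enrolled into one of three groups of 50". Of these, "Participants will be randomized into the 2 technology arms". Group 3 is drawn from residents already tracked in the repository and is asked only for the quarterly questionnaire.

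Under Experiment 6, Procedures, "One hundred and fifty subjects will be followed over a thirty month period". Part 2 of the procedures, directly after enrolment, is "Provide AIMs data (using the web tool from experiment 4) for the transition teams". Part 4 provides for "quarterly Quality of Life assessments" alongside annual clinical assessments. No order is set between part 2 and the first questionnaire.

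Withdrawal of Subjects takes a participant out of the study on moving to a living situation that the study cannot adequately sensor. An exit survey may be requested, but no further OPQOL is mentioned.

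No analysis is given for any Aim 3 outcome. The only methods named, logistic regression and multivariate multiple regression, are in Experiment 2 under Aim 1 and do not mention the OPQOL.

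**The concern.** Two features of the collection plan matter here, because neither can be put right once the trial has run.

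First, a form completed after the team has begun to see AIMs data is a follow-up score, not a baseline. Groups 1 and 2 include existing AIMs participants whose homes may already be equipped, so data sharing could begin soon after allocation and before the first quarterly form falls due. What is lost differs by comparison:

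- Group 1 versus Group 2 is randomised. It stays valid without a baseline but is less precise.
- Group 3 is not randomised. A pre-sharing score is the only direct evidence that it started at a similar quality of life.

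Second, the withdrawal rule depends on whether sensors can be used, but the OPQOL is a questionnaire and needs none. The moves that trigger withdrawal are likely to include transfers to a higher level of care, which are outcome 1. Scores would then be missing after the very event the intervention is meant to prevent. If Group 1 has fewer transfers, as hypothesised, the loss would also differ between the randomised arms. The rule has no clear meaning for Group 3, which has no technology, so follow-up after a move could differ between groups for that reason too.

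**Working it through.** The plan gives no power, effect size or SD, so there is no figure of its own to reproduce. What follows illustrates what a baseline and the repeated forms can be worth for Group 1 versus Group 2.

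**Inputs from the plan.** 50 per group; quarterly forms over 30 months, so 30/3 = 10 follow-up forms if complete.

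**Assumed, because not stated.** Two-sided 5%, 80% power, SD = 1, and the correlation between forms. Clustering by community is ignored.

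**Formula.** Detectable difference = (1.96 + 0.84) × √(2/50 × v) = 0.56 × √v in SD units, where v is the variance relative to one unadjusted form.

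**Equal correlation ρ between any two forms:**

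| Analysis | v | ρ = 0.5 | ρ = 0.6 | ρ = 0.7 |
|---|---|---|---|---|
| One form, unadjusted | 1 | 0.56 | 0.56 | 0.56 |
| One form, baseline-adjusted | 1 − ρ² | 0.49 | 0.45 | 0.40 |
| Mean of ten, unadjusted | (1 + 9ρ)/10 | 0.42 | 0.45 | 0.48 |
| Mean of ten, baseline-adjusted | (1 + 9ρ)/10 − ρ² | 0.31 | 0.30 | 0.27 |

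The last row has v = 0.30, 0.28 and 0.24.

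**Decaying correlation**, r to the power of the number of quarters between forms. Here v for the mean is the average of the 10 × 10 correlation matrix, and adjustment subtracts the square of c = (r + r² + … + r¹⁰)/10. At r = 0.8 the average is 0.543 and c = 0.357, so v = 0.543 − 0.127 = 0.416.

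| Analysis | r = 0.7 | r = 0.8 | r = 0.9 |
|---|---|---|---|
| Mean of ten, unadjusted | 0.36 | 0.41 | 0.48 |
| Mean of ten, baseline-adjusted | 0.34 | 0.36 | 0.35 |

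**The share due to the baseline.** Going from one unadjusted form to ten adjusted forms combines two gains. Use of the repeated forms can be decided later; the baseline cannot. Comparing the last two rows of each table isolates the baseline. It cuts the standard error by 26%, 34% and 43% under equal correlation. Under decaying correlation the cut is √(v adjusted/v unadjusted) subtracted from 1: 6% (0.364/0.416), 13% (0.416/0.543) and 27% (0.384/0.728).

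**An effect that builds.** If the effect grows linearly to its full size at month 30, its average over ten forms is (1 + 2 + … + 10)/(10 × 10) = 0.55 of the final value. The final effect detectable through the average is then 0.27/0.55 to 0.31/0.55, or 0.50 to 0.56 SD from unrounded values, under equal correlation. Under decaying correlation it is 0.61 to 0.66 SD. One unadjusted final form detects 0.56 SD.

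**Selective loss.** The plan gives no rate of moves or withdrawals, so this part cannot be sized.

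**The case against.** A reader might infer that the plan gives up about half of the achievable precision on quality of life. The documents do not support that. They name no Aim 3 analysis, so a comparison of one unadjusted score is not something the plan has chosen; Experiment 6 is headed as a longitudinal evaluation and schedules repeated forms. The near-halving also rests on that comparator, on equal correlation even between forms 30 months apart, and on complete forms. With decaying correlation the reduction in standard error is 36% to 40%. If the effect builds slowly, averaging over follow-up can lose the gain altogether. All of this stands.

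A reader might also infer that there will be no baseline, or that the randomised comparison is invalid without one. Neither follows. The text is silent on the first form, and a quarterly schedule could begin at enrolment. Randomisation protects Group 1 versus Group 2 whether or not a baseline exists.

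Nor would Group 3 be wholly unchecked. It is tracked in the repository, and annual clinical assessments are listed, so other comparability data may exist. The baseline OPQOL is the only direct check on quality of life itself.

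Finally, use of the repeated scores remains open at the analysis stage, and continuing the OPQOL after a move means changing the withdrawal text as well as the timing of a form. Both points are right. Neither removes the two gaps in collection.

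**Conclusion.** The point holds as a gap in what the trial secures. Followed as written, the plan can leave no OPQOL score from before data sharing, and it would end OPQOL follow-up for some participants because they moved. Later analysis cannot recover a missing baseline, and it can address the selective loss only through untestable assumptions.

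The precision figures are conditional. The detectable difference of 0.56 SD for one unadjusted form compares with 0.27 to 0.31 SD (equal correlation 0.5 to 0.7) or 0.34 to 0.36 SD (decaying quarterly correlation 0.7 to 0.9) for ten baseline-adjusted forms. They assume 50 per arm, two-sided 5%, 80% power, complete forms and a steady effect. They show what could be gained and are not a loss built into the plan. The baseline's own share, 6% to 43% of the standard error, depends strongly on the correlation structure, which the documents do not give.

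The change should be made, but this is one of four Aim 3 outcomes and the randomised comparison does not fail without a baseline.

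**What to change.** - In Experiment 6, Procedures, part 4, state that all three groups complete the first OPQOL before the first release of AIMs data to the transition team. For Groups 1 and 2, this should ideally be before allocation is known.
- In Withdrawal of Subjects, separate the end of sensor collection from the end of participation, so that the quarterly OPQOL continues after a move where the participant agrees. Apply the same rule to Group 3.
- Add an analysis for outcome 4: a repeated-measures model of the follow-up scores with baseline OPQOL, visit, group, group-by-visit and community. Name the Group 1 minus Group 2 contrast in advance, either the follow-up average or month 30, in light of whether the effect is expected to be steady or to build. Report comparisons with Group 3 as non-randomised, alongside the baseline scores.

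The cost is the timing of a form already planned, a small change to the withdrawal rule, some continued questionnaire follow-up and a paragraph of analysis text. No new instrument or extra participants are needed. The main downside is that a follow-up average dilutes an effect that builds slowly, which is why the contrast must be chosen deliberately.

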Aim 3: 100 participants (including any continuing participants from Aim 1) will be enrolled into the technology arms. 50 additional participants for the non-technology arm of Aim 3 will be tracked through the ORCATECH repository (IRB#6845) and consented to complete occasional surveys.

RECRUITMENT METHODS

Aim 1: Current participants in Life Lab have consented to be contacted about other research opportunities. All eligible Life Lab participants will be contacted by study staff to determine if they have an interest in participating in Aim 1 of the AIMs study.

Aim 1/Experiment 3: We will contact the care team coordinator(s) at partner communities and have them bring together their transition team for a focus group session.

Aims 2&3 Transition Teams: We will contact the care team coordinator(s) at partner communities and have them provide us a list of transition team members.

Aim 3: Presentations about the project will be given at partner sites. Both potential and existing (Aim 1) participants will be invited to the presentations. Interested parties will be consented into Life Lab first and then, if they meet all eligibility criteria, consented into AIMs.

PROCEDURES INVOLVED

Aim 1: Develop a pervasive computing system tuned to identify trends in AIMs data that are predictive of health decline. Implement a software tool for automatically generating these data on a regular basis for review by care transition teams.

In this aim, we will identify AIMs data most likely to inform care transition decisions. Using data collected from the Layton Center/ORCATECH Repository IRB#6845, and working with the care transition professionals from partner communities, we will develop algorithms to derive key AIMs data from our sensor data in a form easily interpreted by transition teams.

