The current ORCATECH platform consists of equipment and software deployed to individual homes in the community. In experiment 4, we will augment this system to include the automated generation of AIMs data for assisting transition decisions. Creating a sharable tool will require additional modularization, since ORCATECH's has grown organically over the past five years. Extensive documentation of how to install, configure, and use the system will be created for new users.

PLANS FOR DISSEMINATION

Documentation for our system will be made publicly available through the ORCATECH website. We will put into place an electronic system for tracking and controlling access to the data and artifacts, where they will be shared according to the Layton Aging & Alzheimer's Disease Center and ORCATECH Research Repository Protocol. This protocol defines procedures for protecting patient and subject confidentiality in compliance with OHSU and HIPAA guidelines, for accessing limited data sets, and for protecting the integrity of original work contributed to the database.

The in-home sensor data is fully annotated with extensive clinical assessments, as well as weekly reports of health changes. We will share derived anonymized AIMs data with the appropriate research community.

APPROACH FOR SPECIFIC AIM 3

Aim 3: Validate the AIMs metrics and the computer-based tool in senior community settings.

In this aim we will gather data to determine if the proactive use of AIMs data in a senior community setting leads to changes in levels of care needed. Within each of our partner communities, there is a team of health services professionals who track the health and ability to live independently of every resident, at all levels of care. Part of their job is to determine if a resident needs additional in-home care (e.g., home care service or medication assistance), or a transfer to a higher level of care (e.g., from independent to assisted living or a nursing home setting). Thus, our outcomes of interest in this aim are:

- 1) The number of transfers to higher (or lower) levels of care. Levels of care to be considered will include living independently, assisted living, and skilled nursing;
- 2) Percentage of days for which medication assistance was provided (where staff set up medications for the resident); and
- 3) Number of days in which the senior received in-home care for ADL or IADL assistance, by either a professional or informal caregiver

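### A move to a setting that cannot be sensored withdraws the participant from the study, so a transfer (an Aim 3 outcome) can end outcome follow-up before month 30

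*Combined protocol and SAP*

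**What the plan says.** All references are to the combined protocol and SAP.

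- Withdrawal of Subjects: "If participants transition into a living situation that we cannot adequately sensor, they will be withdrawn from the study". The only activity named afterwards is optional: "Any participants withdrawing from the study may be asked to complete an exit survey".
- Approach for Specific Aim 3, first-listed outcome: "The number of transfers to higher (or lower) levels of care", across independent living, assisted living and skilled nursing. No outcome is labelled primary. The others are the percentage of days with medication assistance, "Number of days in which the senior received in-home care for ADL or IADL assistance", and OPQOL.
- Experiment 6, Procedures: "One hundred and fifty subjects will be followed over a thirty month period". OPQOL is quarterly.
- Experiment 6, Study Population: "Participants will be randomized into the 2 technology arms". Group 3 has no technology, is tracked through the repository, and is to be contacted about the study only for OPQOL.

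**The concern.** The rule removes the participant from the study, not merely from sensing, and its trigger is a change of living situation, which is what outcome 1 measures. It sits uneasily with the thirty-month follow-up of all 150 subjects. No section provides for collecting outcomes after withdrawal.

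None of the four outcomes is defined by a sensor, and Group 3 is to be followed without any. The reason for withdrawal therefore does not apply to the data that may be lost: later transfers (including returns to lower care, which outcome 1 counts), later medication-assistance days and later OPQOL.

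The rule names no group. Since Group 3 has no sensors, it presumably operates only in Groups 1 and 2. If Group 3 is followed in full, raw transfer counts would be under-recorded in the technology groups relative to Group 3 even if AIMs has no effect.

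**Working it through.** **What the documents supply.** Three groups of 50 (3 × 50 = 150), 30 months, and quarterly OPQOL (10 per person, 500 per group before deaths). They give no transfer rate, no share of moves that trigger withdrawal, no list of settings that cannot be sensored and no Aim 3 analysis model. There is no plan figure to reproduce, and everything below is illustrative.

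**Assumed rates per year.** Home to assisted living 0.05; home to skilled nursing 0.05 (together 10% first upward moves per year); assisted living to skilled nursing 0.20; death 0.04, 0.08 and 0.20 at home, in assisted living and in skilled nursing. Return from skilled nursing, to home and to assisted living: frequent 1.0 and 0.3; slower 0.3 and 0.1; or none. Each upward move ends observation with probability 0.25, 0.5 or 1, and the triggering move is counted.

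**Method.** Expected transfers = sum over states of (expected time observed in the state × transfer rate out of it), over 2.5 years starting at home. Expected times come from the matrix exponential of the rate matrix.

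**A case that can be checked by hand: every upward move triggers.** Observation stays at home until the first upward move or death, at rate 0.05 + 0.05 + 0.04 = 0.14.
- Time observed = (1 − e^(−0.35))/0.14 = 2.109 years.
- Recorded transfers = 2.109 × 0.10 = 0.211 per person.
- Full follow-up, frequent return (matrix calculation): 0.243 upward, 0.328 in all. Shares: 0.211/0.243 = 0.87 and 0.211/0.328 = 0.64.
- Full follow-up, no return: time in assisted living = (0.05/0.14) × [2.109 − (1 − e^(−0.70))/0.28] = 0.111 years. Transfers = 0.211 + 0.20 × 0.111 = 0.233. Share: 0.211/0.233 = 0.905, upward and all alike.

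**Recorded share of transfers**

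| Moves that trigger | Upward, frequent return | All, frequent return | All, slower return | Upward and all, no return |
|---|---|---|---|---|
| A quarter of upward moves | 0.97 | 0.90 | 0.93 | 0.98 |
| Half | 0.93 | 0.81 | 0.87 | 0.95 |
| All | 0.87 | 0.64 | 0.76 | 0.905 |
| Skilled nursing only, always | 0.96 | 0.71 | 0.83 | 1.00 |

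With frequent return, withdrawals per group of 50 are 2.9, 5.7 and 10.5 for a quarter, half and all. Scaling all upward rates by 0.5 to 1.5 moves the all-trigger upward share from 0.93 to 0.82. Per observed person-time, the upward rate is 0.99, 0.99 and 0.97 of its full value, and the all-transfer rate 0.93, 0.86 and 0.72.

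**Technology group versus Group 3, no true effect, Group 3 followed in full.**
- Upward counts: ln 0.97 = −0.03 to ln 0.87 = −0.14. With 50 × 0.243 = 12.1 expected per group, the Poisson standard error is √(1/12.1 + 1/12.1) = 0.41.
- All transfers, all-trigger, frequent return: ln 0.64 = −0.45. Expected counts are 50 × 0.328 = 16.4 and 50 × 0.211 = 10.5, so the standard error is √(1/16.4 + 1/10.5) = 0.40.

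**Group 1 versus Group 2 (frequent return).** With no effect, both groups lose the same share in expectation. With an assumed 30% cut in upward rates, the fully followed ratio of upward counts is 0.698; the recorded ratios are 0.70, 0.71 and 0.725. The largest shift is ln(0.725/0.698) = 0.04. The standard error is √(1/12.1 + 1/8.5) = 0.45.

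**OPQOL.** Allowing for deaths, about 470 assessments are due per group. Those falling after withdrawal are 15, 29 and 56 in Group 2 and 10, 21 and 40 in Group 1. The difference is 5/470 = 1% to 16/470 = 3.4% of assessments due.

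**The case against.** The strongest reply is that little is lost where it matters. The stated hypothesis concerns upward transfers. Of 12.1 expected per group, about 0.4, 0.8 or 1.6 go unrecorded, well inside sampling error. The randomised comparison hardly moves, and the Group 3 comparison is non-randomised anyway. The large losses in all-transfer counts depend on assumed returns from skilled nursing and on short stays triggering withdrawal, whereas the rule can be read as meaning relocation. With no returns and a skilled-nursing-only trigger, no transfer is lost. All of this stands, and it limits the point.

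A second reply is that the data may be captured elsewhere. Community teams "track the health and ability to live independently of every resident, at all levels of care", and for Aim 3 recruits "Interested parties will be consented into Life Lab first and then, if they meet all eligibility criteria, consented into AIMs". The first describes the teams' usual work; no section says the study draws on it after withdrawal. Whether Life Lab or the repository would supply Aim 3 outcomes after withdrawal cannot be determined from these documents. If they do, one sentence saying so would largely settle the matter.

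A third reply is that in-home care days after a move may not be missing at all. That is fair: the outcome is not defined for assisted living or skilled nursing, so the gap there is one of definition.

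**Conclusion.** The point holds as a conflict between the withdrawal rule and the thirty-month follow-up, and it should be fixed. Confidence is high for the text and low for every figure, since all rates are assumed.

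At the assumed base rates, with a quarter to all upward moves triggering, the recorded share is about 0.87 to 0.98 for upward transfers and 0.64 to 0.98 for all transfers, running from frequent return to no return. Against Group 3, the upward shortfall is below sampling error. Only the raw all-transfer count, with every upward move triggering and frequent return, reaches about one standard error.

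A reader might infer three stronger things that the documents do not support:
- That transfers themselves go uncounted. The triggering move can be recorded; only later events are at risk.
- That every transfer ends follow-up. The rule covers only settings that cannot be adequately sensored, and these are not listed.
- That the randomised transfer comparison is biased. It is undistorted in expectation under no effect and shifted by at most about 0.04 log units under the assumed 30% reduction. If AIMs changes transfers, OPQOL loss would differ modestly between Groups 1 and 2, with no established direction of bias.

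**What to change.** Reconcile Withdrawal of Subjects with the Experiment 6 Procedures by replacing the rule with wording such as:

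> If a participant moves to a setting that cannot be adequately sensored, sensor collection ends but the participant stays in the study. Transfers, medication assistance, staff-provided care and death are collected to month 30 from community team or repository records, by the same procedure in all three groups. Quarterly OPQOL continues where the participant agrees. Informal-caregiver help is asked of Groups 1 and 2 only and is compared only between those groups.

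The last sentence respects the limit on contacting Group 3. Also state how medication-assistance and in-home care days are counted after a move to assisted living or skilled nursing, and that follow-up ends if a participant leaves the partner communities and cannot be reached.

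The change affects data collection only, not care. It costs a protocol paragraph, consent wording and some extra contact with residents who have moved. Some OPQOL will still be missing from frail residents.
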